All enrolled participants will need to maintain their pre-screening psychotherapy schedule throughout the trial duration, given that psychotherapy is the standard of care for BPD. Participants entering the study cannot start any type of psychotherapy within 3 months prior to enrollment or throughout the trial duration. Specifically, participants receiving psychotherapy before initiating the study need to remain in psychotherapy throughout the trial. However, those participants not receiving psychotherapy before the study should not initiate psychotherapy during the trial. Participants deemed needing immediate or emergent psychotherapy and those initiating psychotherapy during the study will be discontinued from the trial.

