 - f) Medications known to be UGT inhibitors or inducers should be used with caution (*)
 - (*) UGT Inhibitors (e.g.: adenine, propofol, flunitrazepam, ertugliflozin, ketoconazole, valproic acid, flurbiprofen, silibinin, sodium aurothiomalate, gemfibrozil, deferasirox, probenecid, amitriptyline, indomethacin, ubrogepant)
 - UGT inducers (e.g.: carbamazepine, phenytoin, phenobarbital, rifampicin, testosterone propionate, lamotrigine, primidone, ethinylestradiol, desogestrel, orthosiphon stamineus)

These lists are not intended to be exhaustive. Drug-Drug Interactions (DDI) interactions should be reviewed in the label.

- g) The concomitant use of MAO inhibitors is forbidden 14 days before Screening visit and throughout the study. The concomitant use of other antidepressants in stable dose for at least 2 months before the Screening visit is allowed for the treatment of psychiatric comorbidities (as per inclusion/exclusion criteria) (**).

(**) The MAO inhibitory activity of vafidemstat has only been observed in vitro; data in humans does not support a MAO inhibitory effect at the doses selected in this protocol. Specifically, the MAO inhibitory activity has not been observed in humans at the vafidemstat therapeutic dose range in clinical trials-to-date, but a potential impact at higher doses (e.g., overdose) cannot be ruled out. Therefore, the concomitant use of any drugs for which cases of serotonin syndrome or hypertensive crisis have been reported when in combination with MAO inhibitors should be carefully monitored. The concomitant use with these drugs should be done with caution. At Baseline Visit, participants will be provided with educational material to create awareness around serotonin syndrome.

- h) The concomitant use of typical antipsychotics is forbidden. The concomitant use of atypical antipsychotics in stable dose for at least 2 months before Screening visit is allowed for the treatment of psychiatric comorbidities (as per inclusion/exclusion criteria). In addition, the concomitant use of an atypical antipsychotic medication (e.g., quetiapine) is allowed for the treatment of insomnia AND only at sub-therapeutic dose (e.g., below that typically used to treat schizophrenia).
- i) The concomitant use of mood stabilizers in stable dose for at least 2 months before Screening visit is allowed for the treatment of psychiatric comorbidities (as per inclusion/exclusion criteria) when these medications are prescribed as per their labelled indications.

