4.2. Removal of Participants from Therapy or Assessment

Participants are free to discontinue trial participation at any time. Withdrawal from the trial will not affect or prejudice participants further care or treatment. In addition, participants may be withdrawn from study treatment and assessments at any time, if deemed necessary by the PI or Sponsor.

Potential reasons for withdrawal of participants from this study include, but are not limited to:

- The participant withdraws his or her consent (defined as a participant who explicitly takes back his or her consent)
- The PI considers it, for safety and/or study compliance reasons, in the best interests of the participant that he or she be withdrawn
- Initiation of concomitant medication prohibited by the study protocol (see [Table 2](#))
- Initiation of psychotherapy in psychotherapy naïve participants at baseline
- Discontinuation of psychotherapy in participants receiving therapy at baseline
- Pregnancy
- Participant is lost to follow-up (defined as a participant who fails to comply with scheduled study visits or contact, who has not actively decided to withdraw from the study, and for whom no alternative contact information is available [this implies that at least two attempts have been made to contact the participant])
- Any center personnel break the randomization code for that participant
- The participant attempts suicide or is at significant risk of suicide (either in the opinion of the investigator or defined as a “yes” to suicidal ideation questions 4 or 5 or answering “yes” to suicidal behavior on the C-SSRS during the study)

The reason and date the participant is withdrawn from the study and further treatment with the IMP will be documented in the electronic case report form (eCRF) (e.g., lost to follow-up, consent withdrawn, incorrect enrollment, AEs, etc.).

If a participant is withdrawn from the study, the PI should attempt to complete all study assessments in [Table 1](#) for the EoS Visit.

Participants who withdraw due to an AE should be followed until resolution of the AE, or the PI or delegated center personnel decides that the AE is stable, and the participant does not need further follow-up. All AEs should be followed up according to Section 8 [ADVERSE EVENTS](#).

If a participant is withdrawn from the study, all data collected until the time of withdrawal will be included in the analyses.

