6.1.2. Prohibited/Permitted concomitant medications

Prohibited concomitant medications are shown below in [Table 2](#). These concomitant medications are prohibited for the duration of the study. Washout periods prior to Visit 1 (Screening) are described in [Table 2](#). The administration of these medications during the study treatment will lead to withdrawal of the participants from the study (see Section 4.2).

Any concomitant medications for psychiatric comorbidities (as per inclusion/exclusion criteria) are allowed when these medications are used as prescribed (see [Table 3](#)).

Table 2. Prohibited Concomitant Medication

	Washout period before Screening Visit (weeks)
Anticoagulants (e.g.: acenocumarol, warfarin, apixaban, dabigatran and rivaroxaban) - Only 81 mg acetylsalicylic acid is permitted	2
Short and medium half-life oral benzodiazepines are allowed in occasional short-term prescription. Participants should not take these medications within 24 hours before any study visit	8
Z-drugs (i.e.: zaleplon, zolpidem, zopiclone) are allowed in occasional short-term prescription. Participants should not take these medications within 24 hours	2

	Washout period before Screening Visit (weeks)
before any study visit	
Corticosteroids or immunosuppressant (only inhaled or topical suspension are allowed)	2
Typical antipsychotics	5
Long half-life benzodiazepines	8 - 21
Esketamine (in the past 90 days)	2.5
MAO inhibitors	2

Table 3. Allowed Concomitant Medication to be used with caution

UGT Inhibitors (e.g.: adenine, propofol, flunitrazepam, ertugliflozin, ketoconazole, valproic acid, flurbiprofen, silibinin, sodium aurothiomalate, gemfibrozil, deferasirox, probenecid, amitriptyline, indomethacin, ubrogepant)

UGT inducers (e.g.: carbamazepine, phenytoin, phenobarbital, rifampicin, testosterone propionate, lamotrigine, primidone, ethinylestradiol, desogestrel, orthosiphon stamineus)

Antidepressants in stable dose for at least 2 months before the Screening visit is allowed for the treatment of psychiatric comorbidities when these medications are used as prescribed per the inclusion and exclusion criteria*

Atypical antipsychotics in stable dose for at least 2 months before Screening visit is allowed for the treatment of psychiatric comorbidities *

Mood stabilizers in stable dose for at least 2 months before Screening visit is allowed for the treatment of psychiatric comorbidities when these medications are prescribed as per their labelled indications*

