7.7.11. Classification of participants according to completion of study visits

According to the number of visits, participants can be classified as follows:

- a. *Completers*: Participants completing Visit 9.

- b. *Non-completers*: Participants that received at least one dose of study treatment, but prematurely discontinued the study before completion of Visit 9 for any reason other than withdrawal of the informed consent. These participants will be asked to complete an End of Study (EoS) Visit as soon as possible after withdrawal. Non-completers will not enter the 2-week participant-blind placebo run-out period.
 - i. If there has been, at least, one week between the last intake of study drug and this EoS visit, no further Safety follow-up visit will be required.
 - ii. If there has been less than one week between the last intake of study drug and EoS visit, participant will be asked to attend to a Safety-follow up visit, two weeks after the last intake of study drug, to perform safety assessments only.
- c. *Non-completers who discontinue the study because they withdraw their consent*: Participants that received at least one dose of study treatment, but prematurely discontinued from the study before completion of Visit 9 due to withdrawal of informed consent. These participants, if possible, will be asked to attend to an EoS Visit.
 - i. The visit must be scheduled as soon as possible after withdrawal.
 - ii. If the participant withdraws consent during a visit but agrees to complete the visit, then, the investigator will complete an EoS Visit. All the data collected up to and including this visit will be used in the analysis.
 - iii. If the participant withdraws consent and refuses to complete the EoS Visit, no new information will be collected. However, it is recommended, outside the scope of this study, to perform a safety assessment within 2 weeks after treatment discontinuation.

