9.3.4. Primary Efficacy Analysis

The primary efficacy analysis will be performed for the CGI-S A/A and the BPDCL scores (sum of responses for all items).

The estimand for the primary efficacy analysis is defined with the target population determined by the inclusion/exclusion criteria, the endpoints targeted are the primary efficacy endpoints for the study and mean changes from baseline to specific weeks as the population level summary. Intercurrent events that are expected to occur include early treatment discontinuation due to patient choice or due to adverse events both unrelated to the medication or study indication (e.g., Covid-19) and related to the study medication or indication, as well as the initiation and/or discontinuation of psychotherapy during the trial.

The mixed model repeated measures (MMRM) will include as fixed factors: site, visit, treatment arm, psychotherapy at baseline, baseline value of the response variable, the interaction between treatment and visit as well as visit interaction with the baseline value (last measurement prior to treatment initiation) for the endpoint and psychotherapy at baseline. The contrast that will be tested for significance is the difference between active treatment and placebo from baseline to specific week. The study is controlled at a 5% level. The Hochberg correction will be applied. If one endpoint is below the 2.5% level or if both endpoints are below the 5% level of significance the study is declared a success.

Possible alternative analysis methods will be investigated as part of the sensitivity analysis, see Section 9.3.11.

Boxplots will be presented for the changes from baseline to specific week in both endpoints by treatment arm.

Descriptive statistics will also be presented.

Full details on the primary analysis will be documented in the SAP and supersede what is outlined in the protocol.

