10.9. Protocol Deviations

The classification of protocol deviations in major or minor deviations will be mutually agreed between the Sponsor and [REDACTED] at the start of the study.

A major protocol deviation occurs when the participant, investigator, or Sponsor fails to adhere to significant protocol requirements affecting selection criteria, administration of study treatment and administration of prohibited medication, including failure:

- To abstain from illicit substance use for at least one-week before the Screening and throughout the trial, as verified by routine drug testing during the trial

- To avoid initiation of any prohibited concomitant medications or psychotherapy during the trial
- To enroll or participate in another investigational study or take any other investigational drug for 3 months prior to and throughout the trial

Failure to comply with GCP guidelines will also result in a major protocol deviation. The Sponsor will determine if a major protocol deviation results in withdrawal of a participant.

Deviations to the study protocol will be documented in a Protocol Deviation Log.

The Sponsor or delegate is responsible for immediately reporting major deviations according to applicable regulations, as well as deviations from the study protocol that substantially affect the integrity or the safety of the participants or the scientific validity of the study, to the CA.

Protocol deviations will be reviewed before interim analysis and database lock in order to allocate the participants into the different analysis sets.

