4.6 Estimands

Summary of primary estimand:

1. In study participants with adult BPD, what is the effect of treatment taken for 12 weeks relative to placebo during the double-blind phase, in the protocol-defined FAS study population as measured by the primary endpoints Clinical Global Impression-Severity focused on agitation/aggression (CGI-SS A/A) and Borderline Personality Disorder Checklist (BPDCL).

2. *Objective*

An estimate of effectiveness which would potentially be supportive of registration. Clinically meaningful effects greater than or equal to 0.2 will be supportive of proof of concept.

3. *Estimand*

- A. The population is the FAS as defined by the protocol's inclusion and exclusion criteria.
- B. Effectiveness is measured using an MMRM to estimate change from baseline over 8-12 weeks in the primary endpoints (CGI-SS A/A and BPDCL).
- C. The treatment evaluated is the randomized treatment as it was assigned to study participants. All types of intercurrent events are incorporated using a treatment policy strategy, which evaluates the randomized treatment as taken including missed or modified treatments, treatment discontinuation, and concurrent treatments. Deaths due to treatment are not expected during the treatment period. A hypothetical strategy will be used to account for the intercurrent event of early study termination to estimate the effect anticipated if all patients had completed the study.
- D. The mean change from baseline between treatment and control arms on the primary endpoints will be estimated over visits associated with 8 -12 weeks of treatment. The study is controlled at a 5% level. The Hochberg correction will be applied. If one endpoint is below the 2.5% level or if both endpoints are below the 5% level of significance the study is declared a success. Intercurrent events that are expected to occur include early treatment discontinuation due to patient choice or due to adverse events both unrelated and related to the medication or study indication (e.g., COVID-19).

4. *Primary estimator and missing data.*

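### Mandatory study withdrawal after new psychotherapy or a prohibited drug leaves most Week 8-12 scores uncollected, although SAP 4.6 makes treatment policy its main strategy

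*Protocol*

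**What the plan says.** **Mandatory.** Protocol 3.1, repeated in 6.1.1 and the synopsis, covers participants who need psychotherapy urgently and adds that "those initiating psychotherapy during the study will be discontinued from the trial". For the drugs in Table 2, section 6.1.2 states: "The administration of these medications during the study treatment will lead to withdrawal of the participants from the study".

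**Discretionary.** Section 4.2, to which 6.1.2 refers, lets the PI or Sponsor withdraw a participant when they judge it necessary. It lists a prohibited drug and new psychotherapy under the words "Potential reasons for withdrawal of participants from this study include, but are not limited to". It also lists stopping baseline psychotherapy, for which no section makes withdrawal mandatory. Section 10.9 classes starting a prohibited drug or psychotherapy as a major deviation and then says: "The Sponsor will determine if a major protocol deviation results in withdrawal of a participant".

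**After withdrawal.** Section 7.7.11 recognises completers and study non-completers only. Of non-completers it says: "These participants will be asked to complete an End of Study (EoS) Visit as soon as possible after withdrawal". Some also attend a later visit for safety assessments alone.

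**Estimand.** Protocol 9.3.4 counts among the expected intercurrent events early treatment discontinuation "as well as the initiation and/or discontinuation of psychotherapy during the trial". SAP 4.6 applies to all types of intercurrent event a "treatment policy strategy, which evaluates the randomized treatment as taken including missed or modified treatments, treatment discontinuation, and concurrent treatments". It gives early study termination a separate, hypothetical strategy. SAP 5.1.1 leaves missing scores to the MMRM, apart from a rule for participants with no post-baseline data.

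**The concern.** Treatment policy asks what the scores were after the event, whatever the participant then took. It can be estimated directly only if those scores are collected. Here the protocol expects the event, the SAP's main strategy covers it, and the withdrawal rule then ends collection. The event is reclassified as early study termination, and the scores are modelled under missing at random (MAR) as if the participant had completed the study.

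The discretionary wording adds a smaller problem. A participant kept under 4.2 or 10.9 contributes observed scores, while one withdrawn under 3.1 or 6.1.2 contributes modelled ones. The trigger is the same, and the outcome depends on which section the site or Sponsor follows. The loss may also be informative, because participants who need psychotherapy urgently are plausibly worsening.

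**Working it through.** **Scale of the plan.** An effect of 0.51, two-sided alpha of 0.025 and 80% power give 74 per arm (normal approximation) or 75 (t-test). The plan states 75. Then 75/0.8 = 93.75, so 94 per arm and 188 in total, as stated. The approximate standard error of the effect is √(2/75) = 0.163 SD.

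**Inputs.** Table 1 puts post-baseline visits through Week 12 on Days 15, 29, 43, 57, 71 and 85; Weeks 8, 10 and 12 are the last three. SAP 4.2 assigns an early-termination assessment to the closest scheduled visit, so the boundaries around these visits are Days 50, 64 and 78.

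**Assumptions not in the documents.** Event days are spread evenly over the 84 days from Day 1 to Day 85, and 5% to 10% of participants have an event.

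**Scores lost when the participant leaves**

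- Case A, EoS visit on the event day. No Week 8-12 score if the event falls before Day 50: 49/84 = 58%. Mean assessments lost: (49×3 + 14×2 + 14×1)/84 = 189/84 = 2.25 of 3.
- Case B, event found and EoS visit done at the next scheduled visit. No Week 8-12 score if the event falls before Day 43: 42/84 = 50%. Mean lost: (42×3 + 14×2 + 14×1)/84 = 168/84 = 2.0 of 3.
- 5% of 188 is 9.4 participants, of whom 4.7 (B) to 5.5 (A) have no Week 8-12 score. 10% is 18.8, giving 9.4 (B) to 11.0 (A).

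**Shift in the estimate.** If leavers are modelled under MAR, the target stays at about 0.51. If they stop study drug but stay in follow-up, the effect is 0.51 × (1 − s·p·f). Here p is the event rate, f the fraction of effect lost off drug, and s the share of Week 8-12 visits that fall after the drug stops:

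- A: s = (56×3 + 14×2 + 14×1)/252 = 210/252 = 0.833.
- B: s = 168/252 = 0.667.

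| Effect lost (f) | p = 5% (B / A) | p = 10% (B / A) |
|---|---|---|
| None | 0.510 / 0.510 | 0.510 / 0.510 |
| Half | 0.502 / 0.499 | 0.493 / 0.489 |
| All | 0.493 / 0.489 | 0.476 / 0.468 |

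The shift from 0.51 is therefore 0 to about 0.02 SD with up to half the effect lost, and up to 0.04 SD with full loss at 10%.

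**Without a drug stop.** The current text does not require a participant who is kept to stop study drug for these events. Suppose new psychotherapy adds 0.3 SD and starts in 10% on placebo and 5% on active. The effect is then 0.51 − 0.3 × 0.05 × s = 0.500 (B) or 0.498 (A), a shift of about 0.01 SD.

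**The case against.** The strongest reply is that the event-specific rules in 3.1, 6.1.1 and 6.1.2 govern these events, while 4.2 and 10.9 are general clauses covering everything from pregnancy to GCP failures. On that reading withdrawal is always mandatory, and SAP 4.6 has a strategy ready for it. Limiting confounding by psychotherapy, the standard of care, is also a legitimate design aim.

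Much of this stands. A reader might infer that SAP 4.6 contradicts itself by giving one event two strategies. It does not: it assigns them to two differently named events, concurrent treatment and early study termination. Nor do the documents show any participant kept in the study after such an event.

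What does not fall away is the data gap. The more consistently withdrawal is applied, the fewer scores treatment policy has for events it is meant to cover.

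The SAP also has partial cover. Placebo-based imputation and the tipping-point analysis address leavers (4.6, 5.1.1.1). Analyses with and without data affected by major deviations, and the per-protocol set, address anyone kept (4.4.2, 4.5). Disposition tables give discontinuations by arm and reason (4.4.1). None of these supplies an observed score after the event.

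Finally, most of the shift calculated above describes stopping drug and keeping the participant, which is the proposed rule. It compares two targets and does not measure an error in the planned analysis.

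**Conclusion.** The point holds as a cheap improvement of small and unknown size. The withdrawal rule moves expected events from the SAP's main strategy into the hypothetical one, and the protocol is inconsistent on whether withdrawal is required. Under evenly spread events at assumed rates of 5% to 10%, about 5 to 11 of 188 participants would lack a Week 8-12 score. The estimate would probably differ by 0 to 0.02 SD, and by up to 0.04 SD with full loss of effect, which is about a quarter of its standard error (0.04/0.163).

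A reader might infer a serious loss of effect or power, and the documents do not support that. An effect of 0.425 to 0.44 needs a 20% event rate, meaning that all planned dropout is of this kind, with immediate full loss. A cruder model with the effect absent at all three visits gives 0.51 × 0.95 = 0.485 or 0.51 × 0.90 = 0.459, with power of 77% or 72% against 81%. It ignores every event that occurs after Week 8 scores are in. No rates or timings in the documents favour either case.

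**What to change.** **Preferred: a protocol amendment that separates stopping study drug from leaving the study.**

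1. In the synopsis, 3.1, 6.1.1 and 6.1.2, where discontinuation is now mandatory, require study drug to stop. Unless they withdraw consent, keep these participants on the Table 1 safety, CGI-S A/A and BPDCL assessments through Week 12. Mandatory stopping preserves the present protection for drugs such as MAO inhibitors, on which exclusion criterion 12(g) says: "The concomitant use of MAO inhibitors is forbidden 14 days before Screening visit and throughout the study".
2. Keep participants who stop baseline psychotherapy in follow-up as well, but without a new mandatory drug stop. Section 4.2 now gives this only as a possible reason for withdrawal.
3. Align 4.2 and 10.9, and add an *off IMP, on study* class to 7.7.11.
4. State in 6.1.2 that the occasional benzodiazepine and Z-drug use permitted in Table 2 does not trigger the rule.
5. Report by arm the participants already withdrawn for these events and how many lack a Week 8-12 score, and state that they fall under the hypothetical strategy.

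No visits or procedures are added. The cost is an amendment across about 20 sites that helps only participants still in follow-up. SAP 4.8 shows that the interim has taken place, and the synopsis plans last patient out for Q4 2023. Earlier and later participants would also fall under different strategies, which is why item 5 is needed.

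**If no amendment of retention is feasible:** align 4.2 and 10.9 with the mandatory rule and add one sentence to SAP 4.6 placing these events under the hypothetical strategy. This removes the inconsistency but gives up treatment policy for them.
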